#### **5.4.3 Management of Results**

Subjects will be contacted if a clinically actionable gene variant is discovered. Clinically actionable findings for the purpose of this study are defined as disorders appearing in the American College of Medical Genetics and Genomics recommendations for the return of incidental findings that is current at the time of primary analysis. Subjects will be contacted at this time with a request to provide a sample to be sent to a CLIA certified laboratory. If the research findings are verified in the CLIA certified lab, the subject will be offered the opportunity to come to NIH (at our expense) to have genetic education and counseling to explain this result. If the subject does not want to come to NIH, a referral to a local genetic healthcare provider will be provided (at their expense).

This is the only time during the course of the study that incidental findings will be returned. No interrogations regarding clinically actionable findings will be made after the primary analysis.

**Note:** incidental findings considered clinically relevant will be discussed among Senior Scientific Staff at meetings such as the weekly UOB conference prior to being communicated to subjects.

#### **5.4.4 Genetic counseling**

Genetic counseling will be recommended should any clinically relevant incidental findings be discovered and consultation with the NCI Genetics Branch will be offered.

## **6 DATA COLLECTION AND EVALUATION**

### **6.1 DATA COLLECTION**

The PI will be responsible for overseeing entry of data into a 21 CFR Part 11-compliant data capture system provided by the NCI CCR and ensuring data accuracy, consistency and timeliness. The principal investigator, associate investigators/research nurses and/or a contracted data manager will assist with the data management efforts. Primary and final analyzed data will have identifiers so that research data can be attributed to an individual human subject participant.

All AEs, including clinically significant abnormal findings on laboratory evaluations, regardless of severity, will be followed until return to baseline or stabilization of event. Document AEs from the first study intervention, Week 1/Day 1, through 90 days after the last administration of the study intervention. After 90 days, only adverse events which are serious and related to the study intervention need to be recorded.

An abnormal laboratory value will be considered an AE if the laboratory abnormality is characterized by any of the following:

- Results in discontinuation from the study
- Is associated with clinical signs or symptoms
- Requires treatment or any other therapeutic intervention
- Is associated with death or another serious adverse event, including hospitalization.
- Is judged by the Investigator to be of significant clinical impact
- If any abnormal laboratory result is considered clinically significant, the investigator will provide details about the action taken with respect to the test drug and about the patient's outcome.

**End of study procedures:** Data will be stored according to HHS, FDA regulations and NIH Intramural Records Retention Schedule as applicable.

**Loss or destruction of data:** Should we become aware that a major breach in our plan to protect subject confidentiality and trial data has occurred, this will be reported expeditiously per requirements in section [7.2.1](#).

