courses are often best served by radical cystectomy. Therefore, cystectomy is recommended for CIS and high-grade Ta and T1 patients who experience disease recurrence following intravesical therapy. However, Shabsigh et al. reported that 64% of patients who undergo cystectomy suffer at least one complication within the first 90 days after surgery and the operation has been reported to have at least a 2.5% perioperative mortality rate even at a high-volume center. For patients unable or unwilling to undergo cystectomy, treatment options are limited.

High grade non-muscle invasive bladder cancer tends to respond well to BCG and when it does not, there is evidence to suggest an incomplete or inefficient immune response. Immune responses directed against tumors are one of the body's natural defenses against the growth and proliferation of cancer cells. However, over time and under pressure from immune attack, cancers develop strategies to evade immune-mediated killing allowing them to develop unchecked. One such mechanism involves upregulation of surface proteins that deliver inhibitory signals to cytotoxic T cells.

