Tumor CT/CT urogram or MRI/MRI urogram of abdomen and pelvis 	X							Every 12 months while on study

SCHEDULE OF STUDY ASSESSMENTS: Screening (Weeks -12 to -1), Induction Phase (Weeks 1 – 12), and Post-Induction Evaluation (All assessments can be performed within +/- 7 days of scheduled assessment to accommodate holidays and scheduling difficulties)									
Assessments to be performed at the times stipulated in the table and as clinically required in the management of the subject  .	Screening	Baseline	All assessments to be performed pre-infusion unless stated otherwise						Post-Induction and Maintenance
			Week 1	Weeks 2 - 5	Week 6	Weeks 7 - 11	Week 12		
Day	-84 to -1	-7 to 0							
Week	-12 to -1	-1							
Urinary PK for Vicineum		X	X 	X 					
Urinary EpCAM levels		X	X 	X 	X (before Vicineum)	Week 10 (before Vicineum)	X (before Vicineum)		
Follow-up Safety Visits for patients who come off treatment or complete study 								Every month up to 90 days post the last dose of immunotherapy 	

1. May be performed up to 12 weeks prior to enrollment.
2. Pre-menopausal female subjects of childbearing potential only.
3. Dose can be administered within +/- 7 days of scheduled administration to accommodate schedule and holidays.
4. Once weekly intravesical administration for weeks 1-12; Dose can be administered within +/- 7 days of scheduled administration to accommodate schedule and holidays.
5. Full physical examination at screening and/or baseline; targeted physical examination at other timepoints and when clinically indicated.

6. Vital signs will be obtained at a single timepoint at screening and baseline. Subjects will have their blood pressure and pulse measured before, during and after the infusion at the following times (based on a 60-minute infusion):
  - At the beginning of the infusion (at 0 minutes)
  - At 30 minutes during the infusion ( $\pm 5$  minutes)
  - At the end of the infusion (at 60 minutes  $\pm 5$  minutes)
  - In the 1 hour observation period post-infusion: 30 and 60 minutes after the infusion (ie, 90 and 120 minutes from the start of the infusion) ( $\pm 5$  minutes) – for the first infusion only and then for subsequent infusions as clinically indicated.

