### **3.6.2 Off-Study Criteria**

The following are off study criteria that will preclude further follow-up:

- Completed study follow-up period
- Participant requests to be withdrawn from study
- Death
- Patient is lost to follow-up
- Patient enrolled into another clinical study

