## **8.4 SAFETY REPORTING CRITERIA TO THE PHARMACEUTICAL COLLABORATORS**

### **8.4.1 Safety Reporting Criteria to AstraZeneca**

#### **8.4.1.1 Safety Reports sent by OSRO**

All SAEs will be reported, whether or not considered causally related to the investigational product, or to the study procedure(s). The reporting period for SAEs is the period immediately following the time that written informed consent is obtained through 90 days after the last dose of durvalumab or until the initiation of alternative anticancer therapy. The investigator and/or Sponsor are responsible for informing the Ethics Committee and/or the Regulatory Authority of the SAE as per local requirements.

The investigator and/or sponsor must inform the FDA, via a MedWatch/AdEERs form, of any serious or unexpected adverse events that occur in accordance with the reporting obligations of 21 CFR 312.32, and will concurrently forward all such reports to AstraZeneca. A copy of the MedWatch/AdEERs report must be emailed to AstraZeneca at the time the event is reported to the FDA. It is the responsibility of the sponsor to compile all necessary information and ensure that the FDA receives a report according to the FDA reporting requirement timelines and to ensure that these reports are also submitted to AstraZeneca at the same time.

\* A cover page should accompany the MedWatch/AdEERs form indicating the following:

- “Notification from an Investigator Sponsored Study”
- The investigator IND number assigned by the FDA
- The investigator’s name and address
- The trial name/title and AstraZeneca ISS reference number (ESR-##-#####)

\* Sponsor must also indicate, either in the SAE report or the cover page, the causality of events in relation to all study medications and if the SAE is related to disease progression, as determined by the principal investigator.

\* Send SAE report and accompanying cover page by way of email to AstraZeneca’s designated mailbox: [[contact]](mailto:[contact])

If a non-serious AE becomes serious, this and other relevant follow-up information must also be provided to AstraZeneca and the FDA.

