## 10 STATISTICAL CONSIDERATIONS

### 10.1 STATISTICAL HYPOTHESES

#### **Primary endpoints:**

The primary objective of this trial is to determine whether the use of a combination of Vicineum and durvalumab in patients with high grade NMIBC previously treated with BCG is safe and tolerable as determined by a 3+3 dose de-escalation trial design. The primary endpoint will be the fraction of patients who have adverse events.

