#### **10.4.2 Analysis of the Primary Endpoint**

All patients will be evaluated for the grades of toxicity identified, and the number of patients will DLTs at each dose level will be reported. The MTD will be identified based on being the dose level at which 0 or 1 patient in 6 has a DLT. All toxicities will be tabulated for all 24 or more patients to be enrolled onto the trial.

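### The 90-day adverse-event window in Section 6.1 is undercut by the visit anchor, the other-study rule in 3.6.2, and the pooling of events after surgery or new therapy

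*Combined protocol and SAP*

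**What the plan says.** Section 6.1 defines the recording period: "Document AEs from the first study intervention, Week 1/Day 1, through 90 days after the last administration of the study intervention". It continues: "After 90 days, only adverse events which are serious and related to the study intervention need to be recorded". It has no stop at surgery or at new anticancer treatment. Section 8.2 sends the reader to 6.1 for the recording timeframe.

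The visits at which late events would be found are timed differently. The calendar in Section 3.4 schedules follow-up safety visits "Every month up to 90 days post the last dose of immunotherapy". Its footnotes 13 and 14 and the post-treatment paragraph of the précis also count from immunotherapy. Section 3.6 counts the same 90 days from the last study therapy, and 3.6.1 from the last study drug.

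Section 3.6.2 lists the criteria that preclude further follow-up. One is "Patient enrolled into another clinical study", with no exception for the 90 days.

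On analysis, Section 10.1 says: "The primary endpoint will be the fraction of patients who have adverse events". Section 10.4.2 says: "All toxicities will be tabulated for all 24 or more patients to be enrolled onto the trial". Neither these sections nor 10.4.4 state a window or refer to 6.1.

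**The concern.** Safety is the primary objective, so the period over which events are collected and tabulated should be the same wherever it appears. If visits are timed from one drug while the recording window runs from the last dose of either, late events may be under-ascertained for the drug given more often. If entry to another study ends follow-up, the patients most likely to leave early are those whose disease has failed.

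The same patients may also have surgery inside the window. Section 3.6.1 stops treatment at high-grade recurrence, and Section 3.3.2 says that high-risk disease would lead to cystectomy. Section 1.2 reports that "64% of patients who undergo cystectomy suffer at least one complication within the first 90 days after surgery". Under 6.1 as written, such complications within 90 days of the last dose are recorded and then tabulated with on-treatment toxicity. Both mechanisms make the safety data depend on disease outcome.

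**Working it through.** **Passages side by side**

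| Place | Start | 90 days counted from | Early stop | Purpose |
|---|---|---|---|---|
| 6.1 | first dose | last study intervention | none | AE recording |
| 6.2.3 | first dose of either drug | not stated | none | toxicity evaluability |
| 8.2 | first dose (SAEs to sponsor) | refers to 6.1 | none | AE/SAE recording |
| Précis; 3.4 and footnotes 13–14 | – | last immunotherapy | none | safety visits |
| 3.6 | – | last study therapy | none | safety visits |
| 3.6.1 | – | last study drug | none | post-treatment assessments |
| 3.6.2 | – | – | entry to another study | end of follow-up |
| 8.4.1.1 | consent | last durvalumab | new anticancer treatment | SAE reports to one collaborator |

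The start is the same in every row that governs recording or evaluability. The anchor wording is not the same, and 3.6.2 has a stop that 6.1 lacks.

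**Effect of the anchor.** Inputs: durvalumab every 4 weeks in year 1 and every 3 months in year 2 (3.2.1.1); Vicineum every other week in maintenance (3.2.2.1). Let L be the number of weeks from the last durvalumab dose to the last Vicineum dose. L is an assumption, because the dosing symbols in the schema are not legible. If *immunotherapy* means durvalumab, scheduled follow-up after the last Vicineum dose is 90 − 7L days.

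- Year 1, L = 0 to 4: from 90 to 90 − 28 = 62 days.
- Year 2, L = 0 to 12: from 90 to 90 − 84 = 6 days. At L = 10 it is 90 − 70 = 20 days.

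The visits could therefore finish up to 84 days before the 6.1 window closes. The duty to record under 6.1 is unchanged; the scheduled contact at which events would be found is what is lost.

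**Effect on a reported rate.** One reclassified patient moves a proportion by 1/24 = 4.2 points with 24 patients, or 1/40 = 2.5 points at the accrual ceiling of 40 (10.2). As an illustration, 12/24 = 50.0% (exact 95% CI 29.1 to 70.9) becomes 13/24 = 54.2% (32.8 to 74.4).

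**Which rates move.** A patient who already had any event on treatment cannot change the any-event fraction. With Vicineum alone, Section 14.2.2.2 reports dysuria in 60.9% of subjects regardless of cause, so many patients will already be counted. A late or surgical event changes counts by type, grade and seriousness. The DLT period is the first 6 weeks (3.1.1), so the DLT count and the dose decision do not depend on the 90-day rules.

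No sample size, power or alpha in the plan depends on this window, so there is no stated figure to reproduce.

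**The case against.** The strongest reply is that 6.1 already gives one window and 8.2 defers to it. That stands. A reader might infer from 8.4.1.1, which runs from consent "through 90 days after the last dose of durvalumab or until the initiation of alternative anticancer therapy", that the primary endpoint has competing start and stop rules. The documents do not support this: that section governs SAE reports to one pharmaceutical collaborator, not recording or analysis.

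Next, no passage says that *immunotherapy* means durvalumab alone. That also stands, and the 6-day figure is conditional on it. Section 3.1.1 uses the word to introduce immune-related events, which points to durvalumab, but Section 1.2 uses it for intravesical BCG. The term needs defining.

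Third, Section 3.6 asks for effort to complete the 90-day visits before a patient is removed from study. Loss on entry to another study is therefore possible, not certain. Effort is still not an exception to 3.6.2, and the two sections remain unreconciled.

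Finally, relatedness is assessed for every event (8.1.5), and an alternate etiology is recorded if the event is unrelated (8.2), so surgical events could be separated. They could, but Section 10 does not say that they will be.

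**Conclusion.** The point holds as an internal inconsistency that should be corrected. The recording window is single and clear; the visit anchor, the off-study rule and the analysis text do not protect it. The largest quantified effect is a year-2 patient with about 6 rather than 90 days of scheduled follow-up after the last Vicineum dose. It rests on two assumptions: that *immunotherapy* means durvalumab, and a 12-week lag. In year 1 the corresponding minimum is 62 days, at an assumed 4-week lag.

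A reader might try to estimate how many patients would carry a surgical complication by applying the 64% to non-responders. The documents do not support such a figure. They give no cystectomy rate for this trial, and some T1 patients qualify because they are unfit for surgery or decline it (2.1.1.1). The 64% also runs from surgery, not from the last dose. Nor can complications of any kind be compared with the 10.0% related Grade 3 or higher rate for durvalumab in Section 1.2.1.2, which is restricted by grade and relatedness.

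The consequence is for tables by type, grade and seriousness. The any-event fraction should move little, and the DLT count is unaffected.

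**What to change.** 1. In 10.4.2 and 10.4.4, cite the 6.1 window as the analysis window.
2. In the précis, the 3.4 calendar row and footnotes 13–14, and Sections 3.6 and 3.6.1, word the anchor as the last dose of either study drug, to match 6.1.
3. Reword 3.6.2 so that AE and SAE collection continues to day 90 after the last dose even if the patient enters another study.
4. Keep every event that 6.1 captures, but show those with onset after cystectomy or new anticancer therapy in a separate row, with relatedness.

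The cost is protocol and SAP wording, CRF fields for the dates of surgery and new therapy, and one extra table row. No data are discarded, and no visits are added beyond those Section 3.6 already asks for. Footnote 15 of the calendar already allows remote evaluation and retrieval of local records, which would help with patients who have moved to another study.

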We would like to continue the drug-combination trial since our preliminary interim data analysis shows a 40% 12 week response rate (5/12 patients) with half of them showing a  $>12$  month sustained response. We hypothesize that the prolonged response might be related to the systemic therapy (Durvalumab) administration. Also, most of the treatment related AEs are irritative voiding symptoms and most of them are grade 3 or lower, suggesting that the treatment is tolerated well thus far. Combination Therapy Dose Justification

In the single-agent phase I Vicineum study, there were no dose-limiting toxicities (DLTs) and no MTD was determined. Only 2 subjects of 64 had detectable plasma Vicineum levels and these were very near the lower level of quantitation. Durvalumab has been extensively studied in Phase I and Phase II and the recommended dose and safety profile has been established. For these reasons, the initial dose level for the combination will be the standard doses for both drugs. The FDA approved dose for durvalumab is currently 10mg/kg every 2 weeks and this amounts to 750 mg every 2 weeks for an average 75 kg individual. Based on pre-clinical data, there is no difference in exposure between weight based Q2W dosing and fixed dose Q4W dosing. Therefore, we are administering 1500 mg every 4 weeks instead of 750 mg every 2 weeks for ease and dosing convenience.

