## **2.2 SCREENING EVALUATION**

Note: Screening evaluation testing/procedures are conducted under the separate screening protocol, 01-C-0129 (Eligibility Screening and Tissue Procurement for the NIH Intramural Research Program Clinical Protocols). Assessments performed at outside facilities or on another NIH protocol within the timeframes below may also be used to determine eligibility once a participant has signed the consent.

Evaluations to be performed within 12 weeks prior to starting treatment:

- History and physical examination (including medications, medical history, surgical history, previous treatments for bladder cancer with dates, allergies, and demography)
- ECOG performance status
- Formal review of available previous bladder tumor specimens by the Laboratory of Pathology, NCI, to confirm the bladder cancer diagnosis prior to enrollment into the study.
  - If outside bladder tumor specimens are inadequate to accurately stage the patient's disease, then additional biopsies will be performed at the NCI as part of standard of care therapy. Tissues obtained at the NCI will be used to confirm diagnosis and for study of immune-related markers. With preoperative patient permission, extra tissue not sent to Laboratory of Pathology, NCI, will be frozen for future analysis of immune-related markers and tumor infiltrates. This additional harvested tissue will be used for research purposes only and is not required for a candidate to participate in this protocol.
  - If outside bladder tumor specimens are adequate to accurately stage the patient's disease, cystoscopy with or without biopsy and/or TURBT to confirm diagnosis and resect and remove any residual papillary disease and fulgurate any CIS may be performed as part of standard of care therapy. With preoperative patient permission, extra tissue not sent to the Laboratory of Pathology, NCI, will be frozen for the future analysis of immune-related markers and tumor infiltrates. This additional harvested tissue will be used for research purposes only and is not required for a candidate to participate in this protocol. Blue light cystoscopy can be performed at urologist's discretion.
- Laboratory studies
  - Hematology (Complete blood count plus differential and platelet count)
  - Serum chemistries and liver function tests (Na+, K+, Cl-, CO2, glucose, BUN, creatinine, albumin, calcium, magnesium, phosphorus, alkaline phosphatase, ALT, AST, total bilirubin, LDH, pre-albumin, amylase, lipase)

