#### **2.4.4 Other Assessments**

- Weight
- Physical Exam, ECOG status, and medications

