### 3.3.2 Vicineum

Following any biopsy or TURBT, study drug must be interrupted for a minimum of 1 week and maximum of 2 weeks before restarting Vicineum treatment. Patients who develop low grade papillary disease will be allowed to stay on trial. In November 2016, the FDA published a draft guidance for trials involving patients with BCG-unresponsive disease in which only high-risk disease counts as a recurrence or an event. In this clinical setting, low-risk disease would lead to transurethral resection while high-risk disease would lead to cystectomy, which is a much different clinical outcome. Therefore, in this trial, low grade recurrences will be documented but will not count as a trial-ending recurrence or event. Furthermore, low grade recurrences are considered to be downstaging of disease since the inclusion criteria requires patients with high grade disease.

Study drug administration must be postponed if a subject develops any Grade 3 or greater adverse event. Study treatment may resume when the AE returns to  $\leq$  Grade 1 or baseline or sooner if there is agreement between the investigator and the sponsor. Study treatment may be postponed at the discretion of the investigator for unrelated AEs, if this is considered in the best interest of the subject. If the causal relationship between Vicineum and an AE is initially uncertain, study drug should be interrupted until that determination is made. Also study treatment may be postponed for lower grade AEs at the investigator discretion if considered in the best interest of the subject.

The following specific criteria will be used for holding Vicineum dosing based on serum creatinine and calculation of creatinine clearance:

Baseline Creatinine	Criteria for Holding Vicineum Treatment*	
	Serum Creatinine	Creatinine Clearance
<1.0 mg/dl or <88 $\mu$ mol/L	>1.5 mg/dl or >133 $\mu$ mol/L	<40 ml/min or a decrease of 25% from baseline
$\geq$ 1.0 mg/dl or $\geq$ 88 $\mu$ mol/L	Increase to $>2 \times$ Baseline Value	<40 ml/min or a decrease of 25% from baseline

\*Vicineum dosing should be held if either the serum creatinine or the creatinine clearance criteria, as defined in this table, are met.

If changes in renal function are noted, the investigator should evaluate the subject for the etiology of these changes. Vicineum treatment may be resumed upon improvement or stabilization at creatinine of  $\leq 2 \times$  baseline or  $\leq 2 \times$  ULN.

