SCHEDULE OF STUDY ASSESSMENTS: Screening (Weeks -12 to -1), Induction Phase (Weeks 1 – 12), and Post-Induction Evaluation (All assessments can be performed within +/- 7 days of scheduled assessment to accommodate holidays and scheduling difficulties)									
Assessments to be performed at the times stipulated in the table and as clinically required in the management of the subject  .	Screening	Baseline	All assessments to be performed pre-infusion unless stated otherwise						Post-Induction and Maintenance
			Week 1	Weeks 2 - 5	Week 6	Weeks 7 - 11	Week 12		
Day	-84 to -1	-7 to 0							
Week	-12 to -1	-1							
Adverse event/serious adverse event assessment			All visits						
Concomitant medications		X	All visits						
ECOG performance status	X	X			X				
Acute care panel 	X	X	X	X	X	X	X	Every 2 weeks	
LDH	X	X	X	X	X	X	X	Every 2 weeks	
Pre-albumin		X							
Pancreatic enzymes (amylase, lipase)	X	X	X	X	X	X	X	Every 2 weeks	

**Abbreviated Title:** Durvalumab & Vicineum for NMIBC

**Version Date:** 05/22/2025

SCHEDULE OF STUDY ASSESSMENTS: Screening (Weeks -12 to -1), Induction Phase (Weeks 1 – 12), and Post-Induction Evaluation (All assessments can be performed within +/- 7 days of scheduled assessment to accommodate holidays and scheduling difficulties)									
Assessments to be performed at the times stipulated in the table and as clinically required in the management of the subject  .	Screening	Baseline	All assessments to be performed pre-infusion unless stated otherwise						Post-Induction and Maintenance
			Week 1	Weeks 2 - 5	Week 6	Weeks 7 - 11	Week 12		
Day	-84 to -1	-7 to 0							
Week	-12 to -1	-1							
Hepatic panel	X	X	X	X	X	X	X	Every 2 weeks	
Mineral panel	X	X	X	X	X	X	X	Every 2 weeks	
Thyroid function tests (TSH and fT3 and fT4) 	X	X		Week 2		Week 6 Week 10		Prior to each durvalumab dose	
Hematology 	X	X		Week 2 Week 4	X	Week 8	X	Prior to each durvalumab dose	
Urinalysis	X	X	X	X (weekly)	X	X (weekly)	X	X (prior to each Vicineum treatment)	
Urine culture and sensitivity		X							

SCHEDULE OF STUDY ASSESSMENTS: Screening (Weeks -12 to -1), Induction Phase (Weeks 1 – 12), and Post-Induction Evaluation (All assessments can be performed within +/- 7 days of scheduled assessment to accommodate holidays and scheduling difficulties)									

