#### **12.4.3 Risks from Bladder Procedures**

Risks associated with cystoscopy, TURBT, biopsies and catheterization include: burning when passing urine, blood-tinged urine, bladder infection or the need to urinate frequently following the procedures. The insertion of a catheter into the bladder through the urethra may cause discomfort. There is also a small risk that these procedures, particularly cystoscopy, TURBT and biopsies, could damage the lining of the bladder or cause a perforation of the bladder. This could lead to urine or drugs leaking out of the bladder causing severe side effects.

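### No urinary symptom grade is scheduled before the first dose, and no rule limits counted events to new or worsened ones, so low-grade symptoms left by TURBT or biopsy can enter the reported urinary AE fraction.

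*Combined protocol and SAP*

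**What the plan says.** Section 6.1 starts AE recording at first treatment ("Document AEs from the first study intervention, Week 1/Day 1") and continues it to 90 days after the last dose. The study calendar in 3.4 agrees: the row "Adverse event/serious adverse event assessment" is empty under Screening and Baseline and begins at Week 1.

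Before dosing, 2.2 schedules a history and physical examination within 12 weeks. Sections 2.4.1 and 2.4.2 add blood tests, urinalysis, cytology and culture within 7 days. Section 2.4.4 adds weight and "Physical Exam, ECOG status, and medications". None of these lists asks for a graded urinary symptom.

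In the same screening window, 2.2 allows "cystoscopy with or without biopsy and/or TURBT to confirm diagnosis and resect and remove any residual papillary disease". Section 2.1.1.1 requires the qualifying biopsy or TURBT for Ta/T1 disease to be within 12 weeks of the first dose and states no minimum interval. Section 12.4.3 lists the after-effects of such procedures as "burning when passing urine, blood-tinged urine, bladder infection or the need to urinate frequently following the procedures". On experience so far in this trial, the text at the end of 1.2.3 reports that "most of the treatment related AEs are irritative voiding symptoms".

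The AE definition in 8.1.1 covers any untoward occurrence, whatever its cause. Section 10.1 makes the proportion of patients with AEs the primary endpoint. Sections 10.4.1, 10.4.2 and 10.4.4 tabulate toxicities by grade and dose level. None of them mentions change from a pre-dose state.

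**The concern.** The trial has one arm, so no concurrent rate can be subtracted. The main toxicity of the instilled drug is urinary, and the procedures that bring a patient into the trial cause much the same complaints. A patient who arrives at Week 1 with mild burning from a recent resection, still has it at Week 2 and is asked about AEs can be recorded as having dysuria on treatment.

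The screening history is not a safe reference point. It may be taken up to 12 weeks before dosing, and so before the procedure that caused the symptom. Two other routes stay open in the exclusion criteria. Urinary infections below Grade 3 do not exclude a patient (2.1.2.4), and one intravesical chemotherapy dose is allowed 28 to 14 days before treatment (2.1.2.9).

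What is at stake is the interpretation of the urinary AE fraction, and of the grade distribution when an existing symptom gets worse.

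**Working it through.** The plan states no figure for this, so there is none to reproduce. The check has two parts.

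**1. Could another provision supply the missing baseline?**

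- Sections 6.1 and 3.4: AE capture begins at the first dose, so a pre-dose symptom is not an AE record.
- Sections 2.2, 2.4.1, 2.4.2 and 2.4.4: history, examination and laboratory tests are scheduled, but no per-symptom grade.
- Section 2.1.2.22: excludes unresolved toxicity of Grade 2 or higher from previous anticancer therapy, with exceptions. This needs a CTCAE judgement, but it is a yes/no threshold. It lets Grade 1 through, schedules no recorded grade, and does not say whether the effects of a TURBT count as toxicity of anticancer therapy.
- Section 8.2: each AE record carries onset date, severity, relationship and, if unrelated, an alternate cause. An onset date can flag a symptom as old. It does not give the grade held before dosing, which is what identifies worsening.
- Sections 10.1 and 10.4: no instruction to drop events with pre-dose onset, or unrelated events, from the endpoint.
- Section 8.4.1.1: the window for reporting serious events to one collaborator opens at consent, but mild urinary symptoms are not serious.

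The gap is therefore partly covered, not closed.

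**2. How large could the effect be?**

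Let *t* be the true treatment-emergent urinary AE rate and *b* the share of patients carrying a symptom over. Assume independence, and that every carried-over symptom persists and is counted. Then

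reported rate = 1 − (1 − *t*)(1 − *b*), and the excess is *b*(1 − *t*).

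The documents give no value for *b*; 10% to 40% is my assumption. For *t*, 14.2.2.3 gives 35% for related renal and urinary disorders in Phase 3, and 1.2.2.2 gives 50% for related dysuria in Phase 2. I use 40%, with those two as neighbours, in 24 patients:

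| True rate *t* | *b* = 10% | *b* = 40% | Patients of 24: true → reported |
|---|---|---|---|
| 35% | 41.5% | 61% | 8.4 → 10.0 to 14.6 |
| 40% | 46% | 64% | 9.6 → 11.0 to 15.4 |
| 50% | 55% | 70% | 12.0 → 13.2 to 16.8 |

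For *t* = 40%: 1 − 0.60 × 0.90 = 0.46 and 1 − 0.60 × 0.60 = 0.64. The excess is 0.10 × 0.60 × 24 = 1.4 patients up to 0.40 × 0.60 × 24 = 5.8 patients. Because the excess is *b*(1 − *t*), it shrinks as *t* rises. On the fraction with an AE of any kind it is smaller again, since a patient with any other AE is already counted.

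**The case against.** The case for leaving the plan alone has real weight.

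- Onset date, relatedness and alternate cause are collected (8.1.5, 8.2), and 8.1.1 requires a temporal association with the product. A careful investigator would date a TURBT symptom to before dosing and attribute it elsewhere. This stands as mitigation. It would be wrong to infer that old and new symptoms cannot be separated at all; what is missing is a reference grade and a counting rule.
- Some grading before dosing is implied by 2.1.2.22. Prior intravesical therapy generally needs 28 days of washout (2.1.2.9), and urinalysis and culture give objective information on blood and infection. This also stands. Carry-over from BCG should mostly be Grade 1, and the recent procedure is the likelier source.
- A reader might infer that the return-to-baseline rules cannot operate. The documents do not support that. In 3.3.2 the text "Study treatment may resume when the AE returns to" continues with Grade 1 or lower as an alternative to baseline. The non-immune DLT item in 3.1.1 has the same alternative and ties baseline status to laboratory abnormalities, which are measured. In 6.1, AEs "will be followed until return to baseline or stabilization of event", so stabilization also ends follow-up.
- A reader might also infer that dose decisions are distorted. DLTs are mainly Grade 3 or higher, and toxicity clearly due to another cause is excluded (3.1.1). The Grade 2 symptom clause requires an event that is refractory to maximal intervention or severely limits daily activities. Mild residual dysuria does not meet these.
- The case report form is not among the documents and may already record baseline symptoms. If so, the protocol should say so and the analysis should use it.
- Catheterization and cystoscopy recur on study and cause the same symptoms. A pre-dose grade does not remove that confounding.

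**Conclusion.** The point holds as a limited weakness in data collection and tabulation. Low-grade urinary symptoms left by a procedure before the first dose can be counted as on-treatment AEs, and worsening of an existing symptom has no recorded reference grade. Existing fields and exclusions reduce the effect but do not eliminate it.

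The direction of any bias is upward. Its size cannot be derived from the documents. The 46% to 64% range for a true 40% rests on an assumed carry-over of 10% to 40%, on independence, and on every carried-over symptom being counted. It is an upper bound for those inputs and should not be read as the expected bias. The effect falls on the reported urinary AE fraction. DLT counts, dose-level decisions, sample size and power do not change.

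The change is still worth making. A pre-dose grade cannot be reliably recovered later, and in a single-arm trial it is the only direct way to distinguish existing symptoms from emergent or worsened ones.

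**What to change.** 1. Add to 2.4.4 and the study calendar a CTCAE v5.0 grade (0 if absent) for dysuria, haematuria, frequency, urgency, nocturia, incontinence and bladder pain. Record it at the existing Baseline visit and again before dosing on Week 1/Day 1.
2. In 10.4.1 and 10.4.4, count a urinary event as treatment-emergent only if it is new, or worse in grade, compared with the last pre-dose record. Section 10.4.2 repeats the wording of 10.4.4 and should point to the same definition. Continue to list all AEs under 6.1 as now.
3. Report a table of baseline grade by worst on-treatment grade for each symptom.
4. For patients already treated, abstract the baseline grade from the chart and state how many grades are missing.

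The cost is one case report form page at visits that already take place. Retrospective baseline data will be incomplete, and symptoms from on-study catheterization and cystoscopy will remain mixed with drug effects; the report should say so. No treatment rule needs to change.
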